
Main inclusion/exclusion criteria:
	
Inclusion criteria:
 
 • Is 18 years of age or older • Is willing to complete all study procedures • Study A: Patients undergoing formal nuclear medicine (99mTc-DTPA) glomerular filtration rate testing or willing to have a venous GFR filtration panel (Study A only) • Study B: Has Chronic Kidney disease (CKD) KDIGO criteria or is at risk of CKD due to heart disease or diabetes as determined by physician 
Exclusion criteria:
 
 • Unable or unwilling to give informed consent • Any condition which would make finger prick contraindicated e.g. severe skin conditions, bleeding disorder • Study A: If formal GFR testing has been requested only because estimated GFR is not considered to reflect true GFR (e.g. liver disease)

Statistical methodology and analysis:
	
 • Accuracy compared to venous serum creatinine and 99mTc-DTPA testing or GFR filtration panel will be calculated for POC-Cr capillary blood testing performed by patients and health care professionals. • Total, between-day, and within-day precision will be evaluated by comparing up to four POC-Cr capillary concentrations for at least seven days and compared to day 1 and 8 venous serum creatinine concentrations.

STUDY TIMELINES
	

Study Duration/length
	
End date 30/06/2025

Expected Start Date
	
1/7/20

End of Study definition and anticipated date
	
Last patient completed final study visit

Key Study milestones
	
 • Month 1-28: Recruitment • Month 29: Data analysis • Month 30 Outcome presentation/publication

STORAGE of SAMPLES (if applicable)
	

Human tissue samples
	
N/A

Data collected / Storage
	
Pseudoanonymised data will be stored for 5 years after study completion in secure filing cabinets in the renal research team locked room.

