2 OBJECTIVES

2.1 Primary Objectives

Study A

- To compare estimated glomerular filtration rate (eGFR) using POC-Cr and serum Cr with formal GFR assessment in people of different ethnicities.

Study B

- To conduct an observational cohort study of serial capillary self-testing POC-Cr for at least one week.
- To compare capillary POC-Cr with venous serum enzymatic creatinine concentrations (serum Cr) in people of different ethnicities performed by health care professionals.
- To compare serial capillary POC-Cr compared with single venous creatinine concentration IDMS traceable enzymatic assay.

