3 STUDY DESIGN

Study A: Cross-sectional cohort study

Study B: Observational longitudinal cohort study

Research Ethics Committee approval and R&I approval will be sought for the study. Participants who meet the entry criteria will be recruited and consented by the investigator, or any GCP qualified member of the local research team who has delegated responsibility for study recruitment. Participants will be recruited from King's College Hospital, Royal London Hospital outpatients and wards and nuclear medicine department. Participants will be offered a minimum of 24 hours to reflect on the patient information sheet (PIS), which will be provided during initial discussion. Participants will be selected purposively to include a range of age, gender, ethnicity (at least 50% African/Afro Caribbean), severity of renal disease and clinical settings. Participants in study A will be able to participate in study B if they wish to do so.

Demographics, Body mass index, waist circumference and lean body mass (Fresenius - Body Composition Monitor and clinician estimated), mobility at home, mode of transportation to come to hospital, length and cost of travel, carer details, drug history, number of hospital visits and GP visits per year and reason for laboratory creatinine testing (e.g. monitoring Ig A nephropathy) will be recorded. Data will be transferred following pseudo-anonymisation into a study specific database by the research team.

POC-Cr testing

Capillary POC-Creatinine concentration will be assessed by NovaMaxCreat (NovaBio) and Epoc (Siemens) POC hand-held devices. A quality control will be performed for each POC-Cr device each day by the study nurse and by participants, ensuring the reagent batch conforms the manufacturers' quality specifications. POC reagents will be stored and used following manufacturers' specifications.

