8 STATISTICAL METHODS

Study A: Readings taken with measured with NovamaxCreat and Epoc blood analysis system will be analysed separately. Bland-Altman plots and Passing-Bablok regressions will be generated for POC-Cr concentrations using Stata version 21 or later. The analytical error percentage compared to the reference standards (IDMS enzymatic traceable and 99mTc-DTPA and GFR filtration panel) ($=100 \times ([\text{POC device}] - [\text{reference standard}]) / [\text{reference standard}]$) will be calculated for each POC-Cr recording in each participant. In addition, average analytical error percentage and a 95% confidence interval (95%CI) will be calculated following Clinical Laboratory Standards Institute procedures.¹⁶ Criteria used to check analytical error percentage will be derived from the 'Desirable Specifications for Allowable Total Error (ATE)' database for creatinine (ATE=8,87%)¹⁵ and from the Laboratory Working Group of the National Kidney Disease Education Program (NKDEP) for eGFR (ATE=10%)¹⁷. Although the 10% ATE for eGFR is actually a performance specification for creatinine, it has been used in as an acceptable total error for eGFR.^{18,19,20} Categorical agreement of POC-Cr concentrations with the reference standards will be calculated using the unweighted Kappa statistic. Error analysis using predefined minor and major classification errors will be performed for POC-Cr concentrations. POC-Cr concentrations and reference standards will also be assessed by Deming regression and Pearson's correlation coefficient. Bias offset required will be recorded

Proportion of patients correctly identified to have CKD $eGFR < 60 \text{mls/min/1.73m}^2$ will be reported. Sensitivity and Specificity of different Cr thresholds calculated.

Study B: Number of tests attempted per participant, daily frequency of testing and proportion of successful attempts will be reported. Reasons for unsuccessful attempts and adverse events will be described and quantified if appropriate. Time taken to train per patient will be reported in minutes as median and IQR.

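### The Study A error formula and Deming regression set creatinine concentrations against GFR references, which does not match the eGFR-scale primary objective

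*Protocol*

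**What the plan says.** Section 2.1 gives Study A one primary objective: "To compare estimated glomerular filtration rate (eGFR) using POC-Cr and serum Cr with formal GFR assessment in people of different ethnicities". The quantity under test is eGFR, from two sources.

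Section 3 states what the devices return: "Capillary POC-Creatinine concentration will be assessed by NovaMaxCreat (NovaBio) and Epoc (Siemens) POC hand-held devices".

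Section 8 then defines an error percentage, 100 × ([POC device] − [reference standard]) / [reference standard]. It lists three references: "The analytical error percentage compared to the reference standards (IDMS enzymatic traceable and 99mTc-DTPA and GFR filtration panel". The error "will be calculated for each POC-Cr recording in each participant", and is then averaged with a 95% confidence interval. Two acceptance limits follow, 8.87% for creatinine and 10% for eGFR.

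The other agreement methods are worded as follows:
- "Bland-Altman plots and Passing-Bablok regressions will be generated for POC-Cr concentrations", with no comparator named.
- "Categorical agreement of POC-Cr concentrations with the reference standards will be calculated using the unweighted Kappa statistic".
- "POC-Cr concentrations and reference standards will also be assessed by Deming regression and Pearson's correlation coefficient", followed by the recording of a bias offset.

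The section ends with the proportion correctly classified as having eGFR below 60, and sensitivity and specificity at candidate creatinine cut-offs.

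**The concern.** Creatinine concentration and GFR are different quantities in different units, and one falls as the other rises. Their difference is not an error. Dividing that difference by the GFR does not make it one, because the result still depends on whether creatinine is expressed in µmol/L or mg/dL. The slope and offset of a regression of one on the other have the same defect.

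The error percentage is the only statistic in section 8 tied to a numerical acceptance limit, so it is the natural basis for a statement on accuracy against formal GFR. As worded, it cannot be read against the 10% limit.

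The primary objective also has a second half, eGFR from serum creatinine against formal GFR. In the listed agreement methods the test variable is always the POC device or POC-Cr, and serum creatinine enters only as a reference. The comparison that would separate the device's contribution to error in GFR from that of creatinine-based estimation in general is therefore not among them.

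**Working it through.** No figure in the protocol can be reproduced here: the point concerns the scale of measurement and does not depend on the target of 375 participants.

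**Step 1. Scale of each term in the formula (sections 3 and 8).**

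| Reference | Scale of reference | Scale of POC recording | Difference meaningful? |
|---|---|---|---|
| IDMS enzymatic creatinine | concentration | concentration | yes |
| 99mTc-DTPA | GFR | concentration | no |
| GFR filtration panel | GFR | concentration | no |

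**Step 2. The formula applied literally to an error-free device.** The creatinine/GFR pairs are assumed for illustration, and 88.4 µmol/L is taken as 1 mg/dL. For 120 µmol/L and GFR 55: 100 × (120 − 55)/55 = +118%. In mg/dL, 120/88.4 = 1.36 and 100 × (1.36 − 55)/55 = −98%.

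| Creatinine (µmol/L) | GFR | Error, µmol/L | Error, mg/dL |
|---|---|---|---|
| 70 | 100 | −30% | −99% |
| 100 | 90 | +11.1% | −98.7% |
| 100 | 60 | +66.7% | −98.1% |
| 120 | 55 | +118% | −98% |
| 100 | 30 | +233.3% | −96.2% |
| 300 | 20 | +1,400% | −83% |

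The device is perfect in every row. The size of the result, and in most rows its sign, is set by the unit.

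**Step 3. The same over a whole sample.** Simulation with n = 375. Assumed: GFR mean 60, SD 25, limited to 12–130, and a noise-free relation GFR = 60 × (Cr/C60)^(−b), with C60 from 80 to 130 µmol/L and b of 1.0 or 1.2. Ranges are over these settings.

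| Statistic against GFR | Literal, µmol/L | Literal, mg/dL | After conversion to eGFR |
|---|---|---|---|
| Mean error | +209% to +458% | −93.7% to −96.5% | 0% |
| Readings within 10% | 4.8% to 10.9% | 0% | 100% |
| Deming slope | −2.6 to −6.1 | −0.02 to −0.04 | 1.00 |

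The last column is perfect by construction, because the assumed relation has no noise. It shows that the scale alone causes the literal results. It does not forecast device performance.

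**Step 4. Which methods survive the change of scale.** In the same simulation, kappa for creatinine above C60 against GFR below 60 was 1.00, so kappa works once categories are set on each scale. Pearson's r was −0.80 to −0.83. It is unit-free and shows inverse association, but not agreement.

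**The case against.** The strongest reply is that section 8 itself shows the eGFR scale was intended. It sets a separate 10% limit for eGFR and explains why a creatinine specification is borrowed for it; such a limit makes sense only if errors are computed on eGFR. Section 2.1 names the derived quantity, and the choice of equation may sit in an analysis plan that is not shown. This stands as evidence of intent, and the absence of an equation from the protocol is not the finding. It does not rescue the formula, which is stated for POC-Cr recordings against GFR references. An analysis plan that put this right would depart from the protocol's wording.

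A reader might infer more than the documents support:
- **That all the agreement analyses are invalid.** Bland-Altman and Passing-Bablok name no GFR comparator and fit the creatinine-to-creatinine comparison in section 2.2. Kappa, classification below 60 and the cut-off analyses work across the two scales.
- **That the study cannot show whether the finger-prick departs from laboratory creatinine.** It can: the IDMS assay is the first listed reference, with its own 8.87% limit.
- **That DTPA and panel results will be pooled.** Section 8 lists both as references but nowhere says they will be combined.
- **That every literal value would fail the 10% limit.** In µmol/L, 4.8% to 10.9% of simulated readings fell inside it by coincidence.

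**Conclusion.** The point holds for the percentage error, its mean and confidence interval, and the Deming slope and offset, each against 99mTc-DTPA or the panel. As written, these carry no accuracy information, and they conflict with the 10% eGFR limit beside them and with the primary objective. The serum-creatinine half of that objective is not a test variable in any listed agreement method.

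It would be too strong to conclude that the primary objective will yield meaningless results: the intended scale can be recovered from the text, and the data are unaffected. This is a misstated formula with an unstated conversion, to be corrected before analysis. The conclusion on scale needs no assumption. The sizes quoted rest on assumed creatinine/GFR values and only illustrate it.

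**What to change.** Replace the single formula with two comparisons, each for the two devices separately:

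1. **Concentration scale.** POC-Cr against venous IDMS creatinine: error percentage with the 8.87% limit, Bland-Altman, Passing-Bablok and Deming. Remove 99mTc-DTPA and the panel from this formula.
2. **GFR scale.** eGFR from POC-Cr and eGFR from serum creatinine, by the same equation, each against formal GFR in mL/min/1.73m²: error percentage with the 10% limit, and Deming regression on that scale. Add the within-participant difference between the two errors, which reduces to 100 × (eGFR from POC-Cr − eGFR from serum Cr)/GFR. Show results by reference type (DTPA, panel), since section 3 gives the panel to participants who are not having routine DTPA testing.

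Kappa, classification below 60 and the creatinine cut-off analyses can stay, and Pearson's r should be described as association.

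The cost is wording. Both creatinines, a GFR reference and demographics are already collected (section 3; Table 1), assuming the demographics include whatever the chosen equation needs. Showing results by reference type makes each estimate less precise; the protocol does not say how many of the 375 will have DTPA, so that loss cannot be sized.

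### The 10% eGFR error limit is a creatinine specification, and nothing stops it being applied against formal GFR, where estimating-equation error counts against the device

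*Protocol*

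**What the plan says.** Section 8 (Statistical Methods), Study A, defines one error measure: 100 times the POC value minus the reference value, divided by the reference value. The references are listed together: "The analytical error percentage compared to the reference standards (IDMS enzymatic traceable and 99mTc-DTPA and GFR filtration panel". The measure "will be calculated for each POC-Cr recording in each participant", so it is signed and defined per reading. A summary follows, introduced as an addition to the per-reading errors: "average analytical error percentage and a 95% confidence interval (95%CI) will be calculated", by procedures of the Clinical Laboratory Standards Institute.

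The limits come next. "Criteria used to check analytical error percentage will be derived from" two sources, giving 8.87% for creatinine and 10% for eGFR. On the second the protocol comments: "Although the 10% ATE for eGFR is actually a performance specification for creatinine, it has been used in as an acceptable total error". It does not say which of the three references the 10% limit goes with.

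Section 2.1 makes the comparison of eGFR, from POC-Cr and from serum creatinine, with formal GFR the primary objective of Study A.

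**The concern.** When POC-Cr is compared with serum creatinine, the difference mainly reflects the device and the capillary sample. When POC-Cr is turned into eGFR and compared with DTPA or the panel, the difference also holds the error of the equation that turns creatinine into GFR. The laboratory's own creatinine carries that error too. A limit written for creatinine measurement has no allowance for it.

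The device could therefore be reported as outside its allowable error because of the equation. Opposing device and equation biases could also cancel and flatter a poor device. This matters because formal GFR is the reference in the Study A primary objective and 10% is the only numeric limit given for eGFR.

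The secondary concern is how either limit is applied. ATE bounds the total error of a result, bias and imprecision together. In a signed mean, positive and negative errors cancel, and its confidence interval narrows as n grows. Using the mean against an ATE would test bias alone.

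**Working it through.** The protocol gives no error SD, equation scatter or bias, so there is no figure of its own to reproduce. From the documents: limits of 8.87% and 10%, and n=375 for Study A. All SDs and biases below are assumptions, shown as ranges.

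**1. Perfect device against formal GFR, individual results.** Set POC-Cr equal to serum creatinine, so only equation error remains. With normal, unbiased percentage errors, P(|e| > 10) = 2[1 − Φ(10/SD)].
- SD 15%: 2[1 − Φ(0.667)] = 50.5%
- SD 20%: 2[1 − Φ(0.500)] = 61.7%

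With a lognormal ratio eGFR/formal GFR = exp(b + sZ) and no bias (b = 0), the share within ±10% is 68.4% at s = 0.10, 38.4% at s = 0.20 and 26.2% at s = 0.30. The two models agree closely.

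**2. Perfect device against formal GFR, mean error.** Mean = 100[exp(b + s²/2) − 1]; SD = 100·exp(b + s²/2)·√(exp(s²) − 1); half-width = 1.96·SD/√375.

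| Log-bias b | Mean error, s = 0.10 to 0.30 | Mean (95% CI) at s = 0.20 | Against 10% |
|---|---|---|---|
| 0 | 0.5% to 4.6% | 2.0% (−0.1 to 4.1) | inside |
| +0.10 | 11.1% to 15.6% | 12.8% (10.4 to 15.1) | outside |
| −0.10 | −9.1% to −5.4% | −7.7% (−9.6 to −5.8) | inside |

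With b = 0 the upper confidence limit never exceeds 7.9%. On the mean, then, a perfect device fails only when the equation is biased upward enough.

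**3. Secondary point: the creatinine limit read on the mean.** Unbiased device, n=375, half-width = 1.96·SD/√375; share outside = 2[1 − Φ(8.87/SD)].

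| Assumed SD | 95% CI of mean | Readings outside ±8.87% |
|---|---|---|
| 10% | ±1.0% | 37.5% |
| 15% | ±1.5% | 55.4% |
| 20% | ±2.0% | 65.7% |

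The mean's CI stays inside 8.87% up to SD = 8.87·√375/1.96 ≈ 88%. For 95% of readings to lie within the limit (my assumed share; the protocol states none), the SD must be at most 8.87/1.96 = 4.5%.

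**The case against.** **On the eGFR limit.** The protocol is open about where the 10% comes from and cites precedent, which cannot be checked here. Section 2.1 also sets serum-creatinine eGFR beside POC-eGFR, so a laboratory benchmark for equation error is in the design. That stands, and it makes the fix cheap. But Section 8 does not tie the limit to that benchmark: its error formula is written for the POC device only, and it lists DTPA and the panel among the references.

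**On averaging.** A reader might infer that the limits are checked only on the average signed error. The text does not support this. The error is defined per recording, the mean and CI come in addition, and the criteria refer to the analytical error percentage without naming the average. The protocol also invokes Clinical Laboratory Standards Institute procedures; the one such document in its reference list concerns total analytical error, and its rule cannot be seen here. A required share of readings could properly sit in an SAP. What remains is that the wording leaves the rule open and the only summary named is one that cannot test total error.

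**On the stakes.** A reader might also infer that a pass/fail verdict is the headline result. The protocol declares no success criterion; the objective is to compare. Imprecision would show in the Bland-Altman plots, kappa and classification errors for creatinine, and in Study B's precision analysis, although none is linked to the ATE limits.

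**On combining the two consequences.** It would be wrong to say that one rule both passes an imprecise device and fails a perfect one. The imprecise device passes only on a mean rule. The perfect device fails mainly on a per-reading rule, and on a mean rule only with upward equation bias.

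**Conclusion.** The main point holds. As written, the 10% creatinine specification can be applied to eGFR against DTPA or the panel, where it measures equation and device together. With zero device error, about 50 to 62% of individual results would exceed ±10% if equation scatter has an SD of 15 to 20%. On the mean there is no failure with an unbiased equation, but there is one at a log-bias of +0.10. These figures rest on assumed scatter and bias; the mechanism does not.

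The secondary point is a clarification: the unit to which the limits apply should be stated, because at n=375 the choice could decide the result (tolerable SD about 88% on the mean against 4.5% on a 95%-of-readings rule).

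Both should be settled before the data are analysed. Neither undermines the design, and other planned analyses limit the harm.

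**What to change.** 1. Apply the 10% limit only to POC-eGFR versus serum-eGFR from the same equation, where equation error is shared and a device identical to the laboratory shows zero difference. The transfer is still approximate: if eGFR varies as creatinine to a power of −1.0 to −1.2 (assumed), a +10% creatinine error gives −9.1 to −10.8% in eGFR, and a −10% error gives +11.1 to +13.5%.
2. Against DTPA and the panel, drop the 10% limit. Report the accuracy of POC-eGFR and serum-eGFR side by side, with the paired difference and its 95% CI.
3. Apply 8.87% to individual errors against serum creatinine: the percentage of readings within the limit with a 95% CI, and the central 95% interval of the errors (2.5th to 97.5th percentile). Label the mean and its CI as bias.
4. Carry the same wording into Study B, whose accuracy analysis refers back to Study A.

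The cost is analysis wording, with no new data; both eGFRs are already in the Study A primary objective. The downside is that the device is less likely to be described as within the creatinine specification.

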Recently, use of ethnicity in kidney function testing has been recommended to be removed. New biomarker GFR filtration panels which do not require adjustment for ethnicity have been

demonstrated to provide better estimation of measured GFR and can be performed without the need for costly nuclear medicine assays⁹. In addition, assessment of lean body weight may enhance estimation equations¹⁰ but have not been assessed in combination with POC-Cr testing.

In other chronic diseases, self-monitoring is associated with feelings of security, reassurance, control, high motivation and levels of satisfaction¹¹ and has transformed care for millions of individuals (e.g. glucose testing). Self-monitoring with POC-Cr testing could empower kidney patients to participate in their own care, enable timely intervention at times of deterioration, and reduce unnecessary hospital visits and damage to veins. Home POC-Cr testing has been demonstrated in a small paediatric study to be an acceptable alternative to hospital testing¹².

Self-monitoring with POC-Cr was strongly supported by AAF engagement participants if appropriate self-care material and education is provided and proposed benefits included privacy of personal monitoring or in a faith-based community setting at the individual's convenience. This approach was considered ideal for those identified to have early CKD at screening event with minimal health care professional contact. However, in order to harness the benefits of POC-Cr self-monitoring it will be important to understand and interpret intra-patient variability in capillary blood results, potentially without need for complete alignment with laboratory tests. Conversely, self-monitoring may introduce increased anxiety and requirement for additional interaction with health care services and concurrent understanding of feasibility (training required, number of successful tests) and patient experience (including acceptability of monitoring frequency) of self-monitoring POC-Cr is critical.

Our overall aim is to develop and pilot a UK community-based screening and CKD monitoring program to address health inequalities in CKD, focusing on people from ethnic minority groups.

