Study A: POC-Cr will be assessed using the NovaMaxCreat and Epoc devices. Finger-prick capillary whole blood samples will be taken (0.05 uL for NovaMaxCreat and 0.9 uL for Epoc) using lancets by the research team. Venous serum creatinine for routine care (Isotope Dilution Mass Spectrometry (IDMS) Traceable Enzymatic assay) and ^{99m}Tc-DTPA glomerular filtration rate testing (where available) will be extracted from hospital laboratory databases. Participants not undergoing routine ^{99m}Tc-DTPA glomerular filtration rate testing will also have a 'eGFR filtration panel assessment – Beta-2-microglobulin, cystatin-C (processed by Synlab/ViaPath) and beta-trace-protein concentration (processed by Affinity laboratories), assessment on their venous blood sample.

Participants will be trained to use the POC-Cr device by the research team and time taken recorded and asked to perform one POC-Cr test.

In addition, the Epop Blood Analysis system, will also measure capillary potassium concentrations, which will be compared to serum potassium (taken from the venous blood sample for routine clinical care). This will be tested in the laboratory using the Roche Chemistry Analyser Cobas 8000.

Study B: Participants will be trained to use the POC-Cr device, NovaMaxCreat (NovaBio) by the research team and time taken recorded. Participants will be taught how to perform quality controls. All sample results will be digitally recorded by the device and downloaded after the device is returned. Participants will be asked to do one test at the hospital (with a simultaneous lab creatinine on site for validation), then to self-monitor four times per day (first thing in morning, midday, before evening meal/early evening, before bed) and each test recorded in a paper diary or electronically as desired. Details reported will include date and time of test, test success, device and non-device failures (test results, missed testing and reasons for missed test (e.g. forgot, did not want to test) and adverse events (e.g. pain or infection or prolonged injury after sampling, pre-syncopal or syncopal episode).

For participants who perform finger-prick testing for capillary blood glucose monitoring, both samples (creatinine using NovaMaxCreat and glucose using their usual device) can be taken from the same finger-prick test. However, participants will be advised to take the creatinine sample first.

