Accuracy of self-monitoring for the first and last reading taken by the participant will be assessed as outlined in Study A. Total, between-day, and within-day precision will be evaluated by comparing up to four POC-Cr capillary concentrations for seven days and compared to day 1 and 8 venous serum creatinine concentrations. Mean and standard deviation for each time point during the week, and within the day will be compared by an independent means *t*-test and *F*-test, respectively, using Stata Version 21 or greater. A *p*-value of less than 0.05 will be considered significant.

SUTAQ scale scores, relationships between scales and group differences on scales will be reported and compared with demographics, frequency, success and accuracy of testing.

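### Study B calls the spread of single home readings precision, although that spread mixes measurement error with the participant's own creatinine variation

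*Protocol*

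**What the plan says.** The Study B part of section 8 defines the quantity and the data it comes from: "Total, between-day, and within-day precision will be evaluated by comparing up to four POC-Cr capillary concentrations for seven days", and these are "compared to day 1 and 8 venous serum creatinine concentrations". The statistical methodology row of the study summary repeats the definition. The comparison method follows: "Mean and standard deviation for each time point during the week, and within the day will be compared by an independent means" *t*-test and an *F*-test, where a *p*-"value of less than 0.05 will be considered significant".

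Section 3 fixes when the readings are taken. After one test at the hospital, participants are asked "then to self-monitor four times per day (first thing in morning, midday, before evening meal/early evening, before bed". No time point has a scheduled duplicate. Extra tests are optional and may be prompted by worry about an earlier result, so they are not planned replicates.

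Three other places bear on the point:

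- Section 1 says of home testing that "it will be important to understand and interpret intra-patient variability in capillary blood results".
- Table 2 in section 4 marks a POC-Cr test by a health care professional and one by the patient at both Baseline (Day 1) and the Final Visit (Day 8).
- Section 3 says "A quality control will be performed for each POC-Cr device each day by the study nurse and by participants", and gives batch conformity as its purpose.

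**The concern.** Precision ordinarily means the scatter of repeated measurements of the same quantity. Here the quantity may move between measurements. A reading on waking and one at bedtime differ in meals, hydration and activity, and readings a week apart come from people with CKD or at risk of it. Nothing records true creatinine at the home time points.

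The within-day and between-day figures will thus contain the participant's own variation under a label that reads as a property of the measurement. This matters because section 1 wants intra-patient variability to be interpretable. A reader who takes the reported figure as measurement error will think the test noisier than it is, and the discrepancy is proportionally largest when the measurement is good. The *t*-test and *F*-test compare means and spreads between time points. They do not divide the variance into its sources.

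The protocol itself names the quantity, the data and the tests, so this is not a detail left open for the SAP.

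**Working it through.** The protocol gives no precision target and no derivation for the Study B size of at least 40, so there is no stated figure to reproduce.

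**Inputs from the protocol.** 40 participants, 7 days, up to 4 single readings a day: 40 × 7 × 4 = 1,120 home readings at most. One professional and one patient test at each of two visits: 40 × 2 = 80 pairs at most.

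**Inputs assumed.** Analytical CV (A) of 3 to 10%. Within-person biological CV (B) of 3 to 8%, its variance split equally between within-day and between-day.

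**What the home readings estimate.**

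- Within-day CV = √(A² + B²/2)
- Between-day CV = √(B²/2), plus any day-to-day device drift (taken as zero here)
- Total CV = √(A² + B²)

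| A (%) | B (%) | Within-day (%) | Total (%) | Total ÷ A |
|---|---|---|---|---|
| 3 | 3 | 3.67 | 4.24 | 1.41 |
| 3 | 8 | 6.40 | 8.54 | 2.85 |
| 5 | 5 | 6.12 | 7.07 | 1.41 |
| 5 | 8 | 7.55 | 9.43 | 1.89 |
| 10 | 3 | 10.22 | 10.44 | 1.04 |
| 10 | 8 | 11.49 | 12.81 | 1.28 |

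A simulation of 1,120 readings with A = B = 5% returned 6.13% within-day and 7.07% total, in agreement with the formulas.

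**Why the home readings cannot separate the parts.** Take a within-day CV of 6.12%, a variance of 37.5. It arises from A = 5% with within-day biology of √(37.5 − 25) = 3.54%. It arises equally from A = 3% with √(37.5 − 9) = 5.34%, or from A = 6.12% with none. The between-day figure can be the same in all three cases. More readings of the same kind sharpen the sum but do not divide it.

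**What the same-visit pairs add.** Repeatability SD = SD(professional − patient difference) ÷ √2, after removing the mean operator difference.

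- With 80 pairs there are 79 degrees of freedom, treating pairs as independent. The chi-square 95% limits are 0.87 to 1.18 times the SD.
- With 40 degrees of freedom, about half the pairs, they widen to 0.82 to 1.28.
- In simulation the pairs recovered the assumed analytical CV: 2.99 for 3%, 5.00 for 5%, 6.96 for 7% and 9.94 for 10%.
- With operator scatter of SD 3% in the difference, a true 5% reads as √(2 × 25 + 9) ÷ √2 = 5.43%. The pairs therefore give an upper bound.

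**The case against.** The strongest reply is that the issue is mainly one of labelling. The protocol never writes device precision. Section 1 asks about variability of capillary results within a person, and the home readings measure exactly that. This stands: the planned numbers are valid if named as total within-person variability. But section 8 and the study summary both say precision, and neither has a step that tells the two meanings apart.

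A second reply is that the SAP may handle variance components. It may, but an SAP that follows section 8 inherits the estimator. The last entry in the reference list has a title on within-person biological variation and analytical imprecision, which suggests the distinction was known. The numbers cited in section 8 do not reach that entry.

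Several stronger readings are tempting, and the documents do not support them.

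- *A reader might infer that no threshold for real change could be derived.* The opposite holds. For two independent readings in a stable person, a change limit is about 1.96 × √2 × total CV. At A = B = 5% this is 1.96 × 1.414 × 7.07 = 19.6%. The analytical CV alone would give 1.96 × 1.414 × 5 = 13.9%, which is too narrow.
- *A reader might infer that a good device would fail.* No pass or fail rule is tied to the home spread. The 8.87% and 10% limits in section 8 are total-error limits against a reference, and accuracy of the first and last self-readings is assessed separately.
- *A reader might treat quality control as ready-made precision data.* It is described only for batch conformity, is absent from Table 2, and nothing says its numeric values are kept. Control material also leaves out finger-prick sampling error.
- *A reader might subtract repeatability from home variation and call the remainder biology.* The pairs are taken on site and the home tests are unsupervised, so the remainder also holds errors of home technique and strip handling.

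**Conclusion.** The point holds as one of definition and analysis. The quantity that section 8 calls precision is measurement error plus the participant's own creatinine variation, and the home readings alone cannot separate them. That follows from the sampling scheme and needs no assumed figure.

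The size does rest on assumption. Under the CV ranges above, total precision would exceed analytical CV by a factor of about 1.04 (analytical 10%, biological 3%) to 2.85 (analytical 3%, biological 8%). These factors illustrate a range and are not estimates for the device in this trial. The within-day factor is smaller and depends on how biological variation divides within and between days.

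What is lost is attribution to measurement or to person. The ability to set a change limit is not lost.

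**What to change.** 1. In section 8 and the study summary, report the home-reading spread as total within-person variability of self-tested results, with between-day and within-day components. Do not call it precision. State that it is the input for any change limit.
2. Estimate measurement repeatability separately from the professional and patient tests at the same visits on Days 1 and 8, after removing the mean operator difference. Give the interval with the number of pairs actually obtained, since failed tests and missed visits will reduce the 80.
3. Bring section 3 into line with Table 2. The Study B text describes one participant test at the hospital and does not mention the professional's test. Record whether both tests use the same device and strip lot.
4. Where numeric daily quality-control values are retained, report them as supporting evidence on between-day analytical precision.
5. Describe any excess of home variation over repeatability as biology plus home-use error.

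The cost is wording, one added analysis and, if wanted, keeping the quality-control values. No test, visit or participant is added to Table 2. The downside is that the pairs carry operator scatter and possibly a second device or strip lot, so they bound on-site repeatability from above and say nothing about unsupervised technique.
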